#### **Ad-interim analysis**

Ad-interim reporting, providing the summary tables, may be performed if necessary or required by CIs and/or investigators, or project leader.

## **5 Risk Description and Minimization**

### **5.1 Risks**

The risks involved with this study are similar to those associated to the same class of patient that underwent PTCA procedure to treat Myocardial Infarction.

Patients follow-up do not include invasive test avoiding any added risks.

There should be no additional risks to the patients assigned to this study. All devices will be market released.

### **5.2 Benefits**

All patients will be more closely monitored by physician throughout the duration of the investigation. Patients will be evaluated at pre-determined time points to assess their status. In addition, similar benefits may accrue to future subjects through experience

gained in this clinical study. IMR information should give the possibility to better find the best health solution for patients enrolled in this study and for the future.

### 6.2 Study Investigators

This clinical study will be conducted by qualified investigators who have experience with the use of device. Qualified Investigators are familiar with the PCI optimization by the assessment of stenosis functional evaluation through FFR and with IMR index for the myocardial viability assessment.

#### 6.2.2 Investigator's responsibilities

A Principal Investigator should have experience in and/or will be responsible for:

- Providing signed Investigator/Co-Investigator (s) Agreement;
- Providing signed Financial Disclosure Form of Clinical Investigators;
- Providing appropriate Ethics Committees Approved Patient Informed Consent and Patient Informed Sheet;
- Conducting the clinical investigation in accordance with the signed agreement with SJMI, the investigational plan, all applicable laws and regulations and any

approval conditions imposed by the appropriate Ethics Committees or applicable regulatory authorities where the study is performed;

- Collection and archiving of data obtained prior to procedure, during procedure, at follow-up examinations and after the study has been completed;
- Strict adherence to the Investigational Plan testing requirements to provide for optimal safety and efficacious use of the device under clinical investigation;
- Screening and selecting appropriate patients;

It is acceptable for the Principal Investigator to delegate one or more of the above functions to an associate or co-investigators; however, the Principal Investigator remains responsible for proper conduct of the clinical investigation, compliance with the investigational plan and collection of all required data. The Investigation is not transferable to other centers attended by the Investigator unless prior approval is obtained from SJMI.

In addition to the responsibilities of the Investigators, the study Coordinating Clinical Investigator will:

- Sign off the final version of the study protocol and after modifications to the protocol if any amendment will be required;
- Act as main contact for all study investigators in case of medical questions related to study conduction.

### **6.3 Amendment Procedure**

Non-substantial changes to, or formal clarification of, the clinical investigational plan must be documented in writing, by Sponsor. Major changes to the protocol will be described in a "CIP Amendment". Amendments will be submitted to the relevant EC and to authorities, where required. Approval/favourable opinion from the relevant EC will be required prior to implementation of the amendment.

Any amendment affecting the patient requires patient's informed consent prior to implementation. Amendments will be signed by all signatories of the protocol. By signing the Amendment Signature Page, Investigators acknowledge the content of the Amendment and confirm that they will adhere to the Amendment change. Signature page will be filed in the Investigator Study Binder and in the Study Master File.

### **6.4 Study Boards**

The clinical study will be conducted as up to 20 sites. A complete list of Study Coordinators, Study Sites, Sites Principal Investigators and Institutions (i.e Core Labs, Clinical Event Committee) will be maintained by the Sponsor.

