### 2.4 Study Design

This is a prospective, multicenter study designed to evaluate IMR ability to predict events occurrence, defined as Cardiovascular death, re-MI, re-hospitalization for HF, resuscitation or ICD appropriate shock, during a 1 year follow-up period.

[figure not shown]
Patients will be enrolled in the study at hospital admission after the pathology assessment has been done. All participants will have the culprit lesion treated following clinical practice and guidelines ; Fractional Flow Reserve (FFR) and IMR will be measured after the primary PCI procedure to evaluate treatment success and myocardial viability. Non-culprit lesions will be functionally evaluated through FFR index and will be treated if FFR will show functional stenosis . FFR and IMR will be measured to evaluate treatment success and myocardial viability. Patients will be followed-up at 1m, 6m and 1y periods.

Device used to assess FFR and IMR is already in use in clinical practice at participating centres. The wire is used following indication for use (IFU), guidelines and clinical practice in the selected centers.

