### **3.2.1 Procedures**

Primary PCI is performed as soon as possible, following the center clinical practice, to treat the culprit lesion. Drug Eluting Stent (DES) of choice in the center and required by the lesion anatomy will be used following the usual clinical practice. FFR and IMR will be measured at the end of the procedure.

Staged procedure to treat the non-culprit lesion will be performed before hospital discharge as per normal clinical practice of the center. FFR and IMR will be measured and lesion will be treated only if FFR will show functional stenosis. Distal lesion that can't be crossed with the guidewire will be treated as per clinical practice. Drug Eluting Stent (DES) of choice in the center and required by the lesion anatomy will be used following the normal clinical practice in each center. FFR and IMR will be measured at the end of the procedure. An ECG will be assessed approximately 90 minutes after primary PCI procedure. A TTE (Echo) will be performed before the patient discharge.

Medical therapy during the procedure and at the hospital discharge will be driven by usual clinical practice, guidelines and standard of care recommendations.

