### **3.3.1 One Month In-Clinic Follow Up**

One month In-Clinic Follow Up is performed by investigator or delegates as per standard practice and in accordance with the activities listed in the Table 2.

All information entered in the eCRF is authorized by the principal investigator or delegates. (Refer to “Appendix F for Data Collection Method” and refer to “Appendix G for Case Report Form” for information regarding patient data collected for this investigation).

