### **3.5 Adverse Events**

#### **3.5.1 Definition of Adverse Event, Adverse Device Effect, Serious Adverse Event and Serious, Unanticipated and Anticipated Adverse Device Effect**

For the purposes of the clinical report, St. Jude Medical will classify each adverse events according to ISO 14155: 2011: Clinical investigation of medical devices for human subjects - Good clinical practice.

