### **3.5.3 Procedure for assessing, recording and reporting Adverse Events, Adverse Device Effects, Serious Adverse Events and Serious Adverse Device effects**

Safety surveillance and reporting will be done for all patients enrolled in this study.

Safety surveillance within this clinical investigation and safety reporting, both performed by the investigator, starts as soon as the patient is enrolled in this clinical investigation (date of signature of the informed consent). The safety surveillance and the safety reporting will continue until the last follow-up visit has been performed or the patient is deceased or the patient/investigator concludes his participation into the clinical investigation.

NOTE: If an adverse event is documented at the patient's last follow up visit, both the notification and follow-up information on the AE CRF are to be provided to the sponsor.

- All serious Adverse Events and all Adverse Device Effects (serious or non-serious) are to be documented and reported to the sponsor maximum 3 calendar days after becoming aware of the event.
- Non-serious adverse events documentation and reporting are limited to cardiovascular and neurovascular events and to events endpoints related.

Should an AE occur, record AE information in the hospital records, document the information into the adverse event form as soon as possible. By completing the form, the sponsor will be notified. Refer to Table 1: Data Collection and Appendix F for Data Collection Method. In case of EDC failure, notify Sponsor via Fax ([contact]) or via [[contact]](mailto:[contact]).

Sponsor will be responsible for ensuring the assessment of immediate AE 'reportability' or 'non-reportability' to the competent authorities. All the reported AEs will be documented and reported in a periodic report.

Additional information may be requested, when required, by the sponsor in order to support the reporting of AEs to regulatory authorities and to support AE analysis. The investigator must notify the EC, if appropriate, in accordance with national and local laws and regulations, of the AEs reported to the sponsor.

In case of disagreement between sponsor and investigator in the AE assessment, then both assessments will be reported.

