### **3.7 Patient Death**

In case of patient death, all death information has to be recorded in either hospital records or the patient death worksheet provided for the investigation and immediately entered in the corresponding eCRF and authorized by the principal investigator or delegates (Refer to "Appendix F for Data Collection Method" and refer to "Appendix G for Case Report Form" for information regarding patient data collected for this investigation): it is Investigator's responsibility to inform the sponsor within 72 hours of becoming aware of the death. It is also Investigator's responsibility to notify the ECs, according to their required timelines.

It is Sponsor's responsibility to inform the competent authorities, locally and nationally as required.

The patient death eCRF must always be accompanied with the documentation of pertinent events; furthermore completing the appropriate eCRF (Adverse Event, Death and Termination) must be completed.

The following information will be reported on the patient death eCRF:

- Date of death.
- Place death occurred (e.g. hospital, nursing home, patient's home)
- If death was witnessed
- Cause of death
- Any other circumstances surrounding the death
- Approximate time interval to death from the initiating event (e.g. sudden, non sudden)
- Autopsy report (if performed)

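### Does the primary test need a written rule on who classifies events, and that they do so without knowing IMR?

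*Combined protocol and SAP*

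**What the plan says.** Section 2.2.1 defines the primary endpoint as a composite at one year: cardiovascular death, repeat infarction, readmission for heart failure, and resuscitation or appropriate ICD shock. Section 4.2 tests it with a chi-square against IMR split at the median. Neither section names a classifier.

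The Clinical Event Committee appears once, in 6.4, in a list of bodies: "Institutions (i.e Core Labs, Clinical Event Committee) will be maintained by the Sponsor". No task, masking or final say is stated. Section 3.8 mentions an Adverse Event Committee, whose only stated role is to ask for the study to be held or ended.

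IMR is read at the site. Section 2.4 says "IMR will be measured after the primary PCI procedure to evaluate treatment success and myocardial viability", and 3.2.1 says "FFR and IMR will be measured at the end of the procedure". Section 5.2 adds: "IMR information should give the possibility to better find the best health solution for patients enrolled in this study and for the future". The supplied text does not conceal the value from anyone.

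Sites also record outcomes. For follow-up visits (3.3.1), "All information entered in the eCRF is authorized by the principal investigator or delegates". Death information, including cause, is to be "immediately entered in the corresponding eCRF and authorized by the principal investigator or delegates" (3.7).

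For safety reporting, 3.5.1 says the sponsor "will classify each adverse events according to ISO 14155: 2011", and 3.5.3 says "In case of disagreement between sponsor and investigator in the AE assessment, then both assessments will be reported".

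Appendix A gives criteria for heart failure and for cardiovascular death.

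**The concern.** In this study IMR plays the part that treatment allocation plays in a trial, and the people who know it also report the outcome. Some components leave room for judgement: whether a readmission was mainly for heart failure, whether a death was cardiovascular, and whether an ICD shock was appropriate. If doubtful cases were accepted more readily at high IMR, part of any association would come from labelling and not from prognosis.

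Sections 3.5.1 and 3.5.3 seem to add to this. Sponsor and investigator may each assess an event, both views are reported, and no rule says which is analysed. Under 4.2 the analysis starts once all patients have finished follow-up, when every IMR value and the median are known. The stake is a false-positive rate above the nominal 5% for the study's main claim.

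**Working it through.** **The plan's own figure.** Inputs from 4.1: 7% against 21%, two-sided alpha 0.05, power 85%, equal groups from the median split. With pooled variance and no continuity correction:

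n per group = [1.960 × √(2 × 0.14 × 0.86) + 1.036 × √(0.07 × 0.93 + 0.21 × 0.79)]² / 0.14² = 108.7, so 109 per group and 218 in all.

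This matches 4.1. Then 218 / 0.9 = 242.2, stated as 242. The concern does not touch the sample size.

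**Effect of labelling.** Inputs: 109 per group (218 / 2). The true risk is set at 14% in both groups, the midpoint of the 12–16% in 4.1. Two inputs are pure assumptions, because the documents give no heart-failure share or disagreement rate:

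- b, the share of patients with a borderline reported event: 2% or 4%, about 4 or 9 of 218;
- d, the shift in acceptance away from an assumed 50% when IMR is known: 0.10, 0.25 or 0.50, that is 60/40, 75/25 or 100/0 percent accepted at high/low IMR.

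Recorded risks become 14% − b×d (low IMR) and 14% + b×d (high IMR). Labels changed in total are 218 × b × d. The rejection probability is the exact binomial sum over all tables where the uncorrected chi-square exceeds its 5% limit.

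| b | d | low v high | labels changed | rejection |
|---|---|---|---|---|
| – | 0 | 14.0 v 14.0% | 0 | 5.18% |
| 2% | 0.10 | 13.8 v 14.2% | 0.4 | 5.27% |
| 2% | 0.25 | 13.5 v 14.5% | 1.1 | 5.71% |
| 2% | 0.50 | 13.0 v 15.0% | 2.2 | 7.30% |
| 4% | 0.10 | 13.6 v 14.4% | 0.9 | 5.52% |
| 4% | 0.25 | 13.0 v 15.0% | 2.2 | 7.30% |
| 4% | 0.50 | 12.0 v 16.0% | 4.4 | 13.88% |

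The last row needs the larger share, complete acceptance on one side, complete rejection on the other, and perfect sorting by group. The sample median is not known until the data are complete. A classifier would know the value and the cut-off of 32 quoted in 4.1, but not the patient's final group.

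**How much room the definitions leave.** Appendix A ties a heart-failure readmission to intravenous treatment and excludes readmissions mainly for recurrent ischaemia. Its general definition of congestive failure also asks for at least one of four supporting findings, two of which rest on measured limits. Intravenous treatment and readmission are facts in the chart. Where the definition rests on the treating physician's decision to treat, a masked reader could not undo that decision.

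**Whether the two safety sections offer rival outcomes.** Section 3.5.1 concerns ISO safety categories for the clinical report. The disagreement sentence in 3.5.3 closes a section on reporting events to the sponsor, authorities and ethics committees. Endpoint-related events do pass through the adverse event form, but neither section sets up two values of the composite. What remains is silence on the classifier.

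**The case for a change.** The strongest reply is that the plan rests on few events, so small shifts matter. At 14% of 218, about 30 are expected. A split of 10 v 20 gives p = 0.049; moving to 11 v 20 gives p = 0.081, and to 10 v 19 gives p = 0.073. One contested label can decide a result near the threshold. A sentence giving the listed committee the final, masked decision would need no extra patients or visits. The arithmetic is right. But any test on about 30 events is this sensitive to a single label, masked or not, and masked classification would not remove that.

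A second reply is that knowledge of IMR might change who is admitted and reported, and not only how events are labelled. If heart failure makes up 6% and capture doubles at high IMR, recorded risks are 14% v 20% and rejection is 22%. With an 8% share it is 34%. These are scenarios with chosen inputs and they bound nothing. A rule on classification would not remove this effect, so it is no argument for one.

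It also stands that Appendix A has no criteria for repeat infarction, resuscitation or appropriate shock, and that no rule says whether an undetermined cause of death counts. Naming a classifier would settle neither.

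**Conclusion.** The silence is genuine: the supplied text names no classifier for the composite, gives the listed committee no task, and masks IMR from no one. No change follows, because this is missing operational detail and not a rule that gives a wrong answer. The committee in 6.4 is the natural body to classify endpoints, and a charter may exist outside these documents. An analyst would sensibly use its decisions and say in the report who classified events and what they knew.

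The labelling effect is small: 5.2% to 5.3–7.3% in five of six scenarios, and 13.9% only in a limiting case. This rests on 109 per group, a 14% risk in both groups, borderline shares of 2% or 4%, and acceptance shifts chosen for illustration. A much larger borderline share would weaken the conclusion, but nothing in the documents points to one. Writing the rule in would mean at least a documented clarification or an amendment under 6.3. It would also mean redacted records for about 29 to 39 patients with events (0.12 × 242 = 29.0; 0.16 × 242 = 38.7), plus other reported potential events and deaths, for a gain that is probably slight.

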### **6.5 Ethical Basis**

This study will be conducted according to ISO14155:2011 "Clinical Investigation of medical devices for human subjects – Good clinical practice", as guidance. It will comply with the World Medical Association Declaration of Helsinki concerning medical research and will be carried out in accordance with local legal and regulatory requirements.

An Institutional Review Board (IRB) and/or Medical Ethic Committee (MEC) written approval is required for center participation in this study. According to Italian Laws about

post marketing clinical trials, with marked release medical device (Decreto Legislativo 46/97, art. 14, comma 8 and Decreto legistativo 502/97, art. 7, comma 7, as modified by Decreto Legislativo 37/10), St Jude Medical Italy will have to provide Italian Competent Authority (CA) a communication with all the information concerning the beginning of the study, including the end or interruption date, through MoH website.

In case additional requirements will be imposed by the Ethics Committee or National Competent Authority/National Regulatory Authority, they shall be followed, if appropriate.

All devices used in this investigation have received regulatory approval and are marked release and used within labeling.

## ***6.6 Insurance***

As Sponsor of this study, St. Jude Medical Italy has taken out insurance for all patients participating in this study.

## ***6.7 Study Management***

The study had to be conducted, recorded and reported in accordance with the Clinical Investigational Plan and the applicable laws and regulations.

### **6.7.1 Study initiation visit**

Before any study activities, SJMI personnel will contact the Investigator to discuss the investigational plan and review the data requirements in detail.

### **6.7.2 Monitoring visits**

Centralize monitoring will occur through routine internal data review. This monitoring is designed to identify missing and inconsistent data, data outliers, and potential protocol deviations that may be indicative of site non-compliance. On site monitoring may occur at the discretion of the Sponsor.

### **6.7.3 Competent Authority (CA) Inspections**

The Investigator and/or designate should contact St. Jude Medical Italy, immediately upon notification of impending CA inspection. A clinical monitor will assist and immediately review study documentation with the investigator and/or designate to prepare for the audit.

An investigator who has authority to grant access shall permit authorized CA employees, at reasonable times and in reasonable manner, to enter and inspect any establishment where devices are held (including any establishment where devices are used or where records or results are kept).

An investigator, or any other person acting on behalf of such a person with respect to an investigation, shall permit authorized CA employees, at reasonable times and in a reasonable manner, to inspect and copy all records relating to the study.

An investigator shall permit authorized CA employees to inspect and copy records that identify subjects, upon notice that CA has reason to suspect that adequate informed consent was not obtained, or that reports required to be submitted by the Investigator, to the Sponsor or EC have not been submitted or are incomplete, inaccurate, false, or misleading.

## Appendix A: Abbreviations & Definitions

Abbreviations	Termes
AMI	Acute Myocardial Infarction
AN(C)OVA	Analysis of (Co)Variance
CABG	Coronary Artery Bypass Graft
Class 1A	Evidence and/or general agreement that a given treatment or procedure is beneficial, useful, effective. Data derived from multiple randomized trials or meta-analyses.
CRF	Case Report Form
CVA	Cerebral Vascular Accident
DES	Drug Eluting Stent
ECG	Electrocardiogram
eCRF	Electronic Case Report Form
EFS	Event-Free Survival
ESC	European Society of Cardiology
FFR	Fractional Flow Reserve
Fup	Follow Up
HF	Heart Failure
ICD	Implantable Cardioverter Defibrillator
IMR	Index of Microcirculatory Resistance
LBBB	Left Bundle Branch Block
LV	Left Ventricular
LV EF	Left Ventricular Ejection Fraction
LVESV	Left Ventricular end Systole Volume
LVEDV	Left Ventricular end Diastole Volume
LVESD	Left Ventricular end Systole Diameter
LVEDD	Left Ventricular end Diastole Diameter
MACE	Major Adverse Cardiac Events
NA	Not Applicable
ND	Not Done
NK	Not Known
NYHA	New York Heart Association
OTW	Over The Wire
PCI	Percutaneous Coronary Intervention
PIC	Patient Informed Consent
PIS	Patient Informed Sheet
PTCA	Percutaneous Transluminal Coronary Angioplasty
RA	Right Atrium
RV	Right Ventricular
SD	Standard Deviation
SJM(I)	St Jude Medical (Italy)
SSR	Statistical Study Report
STEMI	ST segment Elevation Myocardial Infarction
TIA	Transient Ischemia Attack
TTE	Transthoracic Echocardiogram
WMSI	Wall Motion Score Index

